7.1. Sample Size Justification Primary Endpoint

A recent single center, non-randomized, retrospective study [Yabe 2018] has shown to achieve 21.9% contrast reduction when using Dynamic Coronary Roadmap compared to the control group without using Dynamic Coronary Roadmap, see Table 1.

	Control group	DCR group
Number of patients	103	43
Iodinated contrast volume (ml) average \pm standard deviation	152.1 ± 73.0	118.8 ± 49.7

Table 1 Results of a recent pilot study [Yabe 2018]

To determine the sample size for the primary endpoint of this study we used the Yabe study outcomes as input with a margin of 7% for the contrast reduction, i.e., the sample size calculation is performed to reliably show a 15% contrast reduction in the DCR group compared to the control group not using Dynamic Coronary Roadmap.

For the sample size and power calculations we have set:

- Estimated mean for the Control group = 152.1 (based on [Yabe 2018])
- Estimated mean for the DCR group = 129.3 (15% reduction)
- Estimated standard deviation = 73.0 (based on [Yabe 2018])

IGT Systems	Post-Market Clinical Study Protocol DCR4Contrast Clinical Evidence Study	Doc ID: XCY612-130576 Rev: 02 Page 18 of 33
-------------	-----------------------------------------------------------------------------	---------------------------------------------------

- Effect size (standardized difference): $(152.1 - 129.3)/73.0 = 0.3123$
- Significance: one-sided $\alpha = 0.025$ (the type I error, i.e., probability of rejecting a true null hypothesis)
- Power $(1-\beta) = 80\%$

Sample sizes of 162 for each group achieves 80% power to reject the null hypothesis of equal means when the population mean difference is 15% with a standard deviation of 73.0 for both groups and with a significance level (alpha) of 0.025 using a one-sided two-sample equal-variance t-test (calculated by PASS 16.0.3 software).

Finally the percentage of subjects that are expected to be lost at random during the course of the study (drop-out rate) and for whom no response data will be collected (i.e., will be treated as "missing") needs to be taken into account. A drop-out rate of 10% (DR=0.1) is assumed, meaning that $162/(1-DR)=180$ patients are needed in each group totaling 360 patients for the primary endpoint.

The study will be a multi-center trial in which per center a maximum of three investigators will be participating and each investigator is required to include at least 20 patients in the study, which indirectly sets the minimum number of subjects to be included per center.

7.1.1. Sample Size Justification Secondary Endpoint

A recent single center, non-randomized, prospective study [Rajappan 2017] showed a 25.6% reduction in the total number of cine X-ray runs after introduction of Dynamic Coronary Roadmap, see Table 2.

	Enrollment group 1	Enrollment group 4
Number of patients	21	21
Number of cine X-ray runs	Average: 46.2 SD: 22.4 Median: 43.0 IQR: 31-54	Average: 34.6 SD: 21.2 Median: 32.0 IQR: 20-43
Number of stents	Average: 1.76 SD: 0.89	Average: 1.67 SD: 0.86

Table 2 Results of a recent pilot study [Rajappan 2017]

For the sample size and power calculations we have set based on [Rajappan 2017]:

- Estimated mean for the Control group = 46.2
- Estimated mean for the DCR group = 34.6
- Estimated median for the Control group = 43.0
- Estimated median for the DCR group = 32.0
- Significance: one-sided $\alpha = 0.025$ (the type I error, i.e., probability of rejecting a true null hypothesis)
- Power $(1-\beta) = 80\%$

Sample sizes of 177 for each group achieves 80% power to reject the null hypothesis of equal population distributions with a significance level (alpha) of 0.025 using a one-sided Wilcoxon-Mann-Whitney test, since the number of angiographic X-ray runs is discrete and is likely to be not normally distributed (calculated by SAS software).

This means for the secondary endpoint on Number of Angiograms that $177/(1-DR)=197$ patients are needed in each group, so 394 in total which is higher than the total number of patients (360) required for the primary endpoint, so **a total of 394 subjects are required for this study**.

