8 STATISTICAL METHODS

8.1 Sample Size

We plan to include 394 subjects in the study, the maximum number of subjects needed for the analysis of the primary and secondary endpoint. We target to limit the enrollment duration of the 394 subjects to a 9 months maximum, which translates to minimally 10 subject inclusions per week overall. Based on a typical PCI procedure volume and the inclusion and exclusion criteria it is feasible to enroll at least 2 subjects per week per center, i.e., at least 5 centers are required.

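### The secondary-endpoint size of 177 per group at 80% power, which sets the trial at 394, rests on an unstated dispersion; with the pilot SDs about 60 per group suffice and 177 gives over 99% power

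*Protocol*

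**What the plan says.** Protocol 7.1.1 takes its inputs from a single-centre, non-randomised pilot with 21 patients in each of the two groups compared. The pilot table (Table 2 in the protocol, Table 3 in the SAP) gives, for the number of cine runs, "Average: 46.2 SD: 22.4 Median: 43.0 IQR: 31-54" before the roadmap was introduced and "Average: 34.6 SD: 21.2 Median: 32.0 IQR: 20-43" after.

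The list of calculation inputs below the table contains the two means (including "Estimated mean for the DCR group = 34.6"), the two medians, the alpha and the power. No SD, IQR, distribution or probability of superiority is listed.

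The result is: "Sample sizes of 177 for each group achieves 80% power to reject the null hypothesis of equal population distributions". The test named is the Wilcoxon-Mann-Whitney, one-sided at the 0.025 level. The only remark on shape is that the count "is likely to be not normally distributed (calculated by SAS software").

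After 10% drop-out this becomes 197 per group, "394 in total which is higher than the total number of patients (360) required for the primary endpoint". SAP 8.1.2 repeats the calculation with the same inputs, and SAP 8.1 describes 394 as "the maximum number of subjects needed for the analysis of the primary and secondary endpoint".

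**The concern.** The power of a rank test depends on how far the two distributions overlap. Means and medians do not fix that overlap; a spread and a shape are also needed. The primary calculation (Protocol 7.1) does list its SD of 73.0, so the omission is particular to the secondary endpoint.

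The pilot difference is 11.6 runs against SDs near 22, a standardised difference of about 0.53. That is far larger than the 0.3123 used for the primary endpoint, yet the secondary endpoint is said to need more patients (177 against 162 per group).

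At stake is the justification of the total. The trial size was raised from 360 to 394 on this figure alone. If it does not follow from the pilot data, the stated 80% is wrong and so is the statement that the secondary endpoint is the larger requirement.

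**Working it through.** **Steps that reproduce.**
- Drop-out: 177/0.9 = 196.7, so 197 per group and 394 in total.
- Primary t-test with standardised difference 0.3123: power is 0.800 at 162 per group, as stated.

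**Inputs.** One-sided alpha 0.025 and power 80%, so (1.960 + 0.842)² = 7.849. Means 46.2 and 34.6 (difference 11.6, or 25.1% of 46.2) and medians 43 and 32 (difference 11) come from the list of inputs. SDs 22.4 and 21.2 come from the pilot table.

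**Formula (Noether).** With P = Pr(control count > DCR count), n per group = 7.849 / [6(P − 0.5)²]. Approximate power at n per group is Φ(√(6n)·(P − 0.5) − 1.960).

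**Normal shape, means.** The SD of a difference between one patient from each group is √(22.4² + 21.2²) = 30.84.
- P = Φ(11.6/30.84) = Φ(0.376) = 0.6466
- n = 7.849 / (6 × 0.1466²) = 60.9
- Power at 177: Φ(32.59 × 0.1466 − 1.960) = Φ(2.82) = 0.998

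**Other shapes matched to the pilot SDs.** The second n uses the variance under the alternative. Simulations used 20,000 runs with counts rounded to integers and a tie correction.

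| Shape | P | n per group (Noether / alternative variance) | Simulated power at 177 |
|---|---|---|---|
| Normal, means | 0.6466 | 60.9 / 58.9 | 0.998 |
| Normal, medians | 0.6393 | 67.4 / 65.4 | 0.997 |
| Logistic, same SDs | 0.6560 | 53.8 / 51.9 | 0.999 |
| Gamma | 0.6631 | 49.2 / 47.2 | 0.9998 |

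At 60 per group, simulated power under the normal shape with the means is 0.807. A lognormal shape matched to the same means and SDs lowers the requirement further, to about 40. After drop-out, 60/0.9 = 66.7 gives 67 per group and 134 in total; the range 47 to 67 gives 106 to 150 in total.

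**What would return 177.** Solving n = 177 gives P = 0.586. Three routes reach it or come near it:
- *Wider spread.* With the listed means and a normal shape, the common SD would have to be about 38, some 1.7 times the pooled pilot SD of 21.8.
- *Smaller difference.* With the pilot SDs, a difference of about 6.7 runs (14.4% of 46.2) matches 177. This contradicts the listed DCR mean of 34.6.
- *A logistic scale.* Logistic distributions centred at 46.2 and 34.6, with 22.4 entered as the scale parameter in both groups, give P = 0.5855 and n = 178.8 (Noether) or 176.9 (alternative variance). The logistic SD is then 22.4 × π/√3 = 40.6 and the IQR width 2 ln(3) × 22.4 = 49, against 22.4 and 23 in the pilot. Such distributions put 11% of control and 18% of DCR counts below zero. This is a possible cause only; the documents do not state it. Under this model 60 per group would have only 37% power, so the unstated dispersion decides the answer.

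**Effect on the primary endpoint.** With 177 evaluable per group, primary power is 0.834 instead of 0.800.

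**The case against.** The strongest reply is that 177 is under-specified and need not be an arithmetic error. The listed inputs fix no sample size, and an exponential model would give 244 to 254 per group, so 177 does not contradict the list taken alone. The pilot is also a weak yardstick. It had 21 patients per group at one centre, in elective PCI, whereas the trial is multi-centre and takes ad hoc PCI as well. From the pilot table the 95% interval for the difference is 11.6 ± 2.02 × 6.73, about −2 to 25 runs, so a difference of 6.7 lies well inside it. A cautious planner might well have allowed for more spread or a smaller effect. The figure is conservative in any case.

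Much of this stands. The cause is unknown without the SAS input, the over-99% figure is conditional on an imprecise pilot, and no conclusion of the trial is endangered. But it does not rescue 177 as written. Both documents say the calculation was based on the pilot and mention no allowance, whereas the primary calculation states its 7% margin openly. A smaller effect contradicts the listed DCR mean. No shape tried that was matched to the pilot means or medians and dispersion comes near 177; across all variants the results stay at about 72 per group or below.

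**Conclusion.** The concern holds. With the pilot means and SDs, 80% power at one-sided 0.025 needs about 60 per group (47 to 67 across normal, logistic and gamma shapes; lower for lognormal), about 134 in total after drop-out, against the stated 177 and 394. Power at 177 is then over 99%, not 80%, and the primary endpoint's 360 is the larger requirement.

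This rests on the pilot dispersion being the intended one. If a wider spread or smaller effect was intended, the defect is that neither document states or justifies it. In both cases the error is conservative: the total is 34 above the primary requirement and neither endpoint is underpowered. What fails is the stated power and the reason given for 394.

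**What to change.** In Protocol 7.1.1 and SAP 8.1.2, state the distribution, the dispersion and the effect entered in SAS to obtain 177. Then:

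- If the pilot dispersion was intended, restate the secondary requirement as about 60 per group (about 134 in total after 10% drop-out). State that 177 evaluable per group gives over 99% power for the secondary and about 83% for the primary endpoint, conditional on the planning assumptions, and that 360 for the primary endpoint is the larger requirement. SAP 8.1 should then agree.
- If a wider dispersion or a smaller effect was intended, state its value and justify it against the pilot table.

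Keep 394 randomised in either case. The cost is a text correction in the two sample-size sections, with no change to enrolment, test, alpha or endpoint.

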7.2. General Considerations

All results will be summarized using descriptive statistics, i.e., using frequencies and percentages or summary statistics like averages and medians (including confidence intervals and interquartile ranges).

IGT Systems	Post-Market Clinical Study Protocol DCR4Contrast Clinical Evidence Study	Doc ID: XCY612-130576 Rev: 02 Page 19 of 33
-------------	-----------------------------------------------------------------------------	---------------------------------------------------

Subgroup analyses (e.g., for 1, 2, 3 or more vessel PCI, and anatomical complexity via SYNTAX score) will be performed and presented. Methods to correct for missing data will be used like, e.g., worst case scenario analysis, multiple imputation methods [Rubin 2004]. Analyses to determine whether there is an effect based on e.g. intervention difficulty, lesion characteristics, patient demographics, physician experience, center effect etc. will be performed. If an effect is found applying adjustment analysis will be considered. An independent angiographic committee of experts may be consulted to blindly analyze cases to check for validity of exclusion and inclusion criteria and other relevant aspects of the study, and potential adjustment analysis will be considered. Statistical analysis will be performed using SAS (SAS Institute, Cary, North Carolina) and/or R statistical software (<https://www.r-project.org/>).

7.3. Poolability

A site effect analysis will be conducted on the primary endpoint to assess poolability of data. Adjustment analysis will be considered if sites are not homogeneous.

7.4. Subject Disposition

Subject disposition, including the total number of subjects evaluated will be presented. In addition, a listing will be provided with the reasons for why the subject was not evaluated.

7.5. Demographics and Baseline Characteristics

Basic subject characteristics such as age, gender, height and weight will be summarized. In addition, the SYNTAX score [Sianos 2005, Neumann 2018] will be determined for the vessel(s) treated with PCI as an index for anatomical complexity, the number of lesions treated in the PCI, the location of the lesion, etc., see Figure 4:

[figure not shown]
Steps	Variable assessed	Description
Step 1	Dominance	The weight of individual coronary segments varies according to coronary artery dominance (right or left). Co-dominance does not exist as an option in the SYNTAX score.
Step 2	Coronary segment	The diseased coronary segment directly affects the score as each coronary segment is assigned a weight depending on its location, ranging from 0.5 (i.e. the posterolateral branch) to 6 (i.e. left main in case of left dominance). 
Step 3	Diameter stenosis	The score of each diseased coronary segment is multiplied by two in case of a stenosis 50-99% and by five in case of total occlusion. In case of total occlusion, additional points will be added as follows: 
 – Age >3 months or unknown +1 – Blunt stump +1 – Bridging +1 – First segment visible distally +1 per non-visible segment – Side branch at the occlusion +1 if <1.5 mm diameter +1 if both <1.5 mm and ≥1.5 mm diameter +0 if ≥1.5 mm diameter (i.e. bifurcation lesion)
Step 4	Trifurcation lesion	The presence of a trifurcation lesion adds additional points based on the number of diseased segments: 
 – 1 segment +3 – 2 segments +4 – 3 segments +5 – 4 segments +6
Step 5	Bifurcation lesion	The presence of a bifurcation lesion adds additional points based on the type of bifurcation according to the Medina classification:126 
 – Medina 1,0,0-0,1,0-1,1,0 +1 – Medina 1,1,1-0,0,1-1,0,1-0,1,1 +2 Moreover, the presence of a bifurcation angle <70° adds one additional point
Step 6	Aorto-ostial lesion	The presence of aorto-ostial lesion segments adds one additional point
Step 7	Severe tortuosity	The presence of severe tortuosity proximal of the diseased segment adds two additional points
Step 8	Lesion length	Lesion length >20 mm adds one additional point
Step 9	Calcification	The presence of heavy calcification adds two additional points
Step 10	Thrombus	The presence of thrombus adds one additional point
Step 11	Diffuse disease/ small vessels	The presence of diffusely diseased and narrowed segments distal to the lesion (i.e. when at least 75% of the length of the segment distal to the lesion has a vessel diameter <2 mm) adds one point per segment number

Figure 4 Steps to determine SYNTAX score as an index for anatomical complexity of the PCI [from Neumann 2018]

IGT Systems	Post-Market Clinical Study Protocol DCR4Contrast Clinical Evidence Study	Doc ID: XCY612-130576 Rev: 02 Page 21 of 33
-------------	-----------------------------------------------------------------------------	---------------------------------------------------

7.6. Primary objective

Objective

To assess whether using Dynamic Coronary Roadmap reduces the total iodinated contrast volume related to PCI compared to the control group without Dynamic Coronary Roadmap.

Endpoint

The primary endpoint of the study is the average total undiluted iodinated contrast volume (in ml) used per PCI (from first positioning the interventional guiding catheter in stable coronary position till end of PCI procedure) measured by an automatic contrast injector.

Hypothesis

Dynamic Coronary Roadmap reduces the total iodinated contrast volume used on average per PCI.

$$H_0: \mu_{Control1} - \mu_{DCR1} \leq 0$$

$$H_a: \mu_{Control1} - \mu_{DCR1} > 0$$

Where $\mu_{Control1}$ is the average total iodinated contrast volume usage per PCI for the Control group, and μ_{DCR1} is the average total iodinated contrast volume usage per PCI for the DCR group.

Rationale for choice of hypothesis

Based on pilot study results and the working mechanism of DCR this hypothesis is chosen to measure the reducing effect of DCR on the total iodinated contrast volume usage in PCI.

Analysis

The objective will be evaluated using a one-sided two-sample equal-variance t-test. The relative impact of the analysis results will be made in comparison to the maximum ratio of contrast volume (in ml) to the glomerular filtration rate (in ml/min/1.73m²) being 3.7 for severe CKD (eGFR<30) as recommended by the ESC/EACTS Guidelines [Laskey 2007, Neumann 2018].

All subjects will be included in this analysis.

7.7. Secondary objective

7.7.1. Secondary objective: Number of Angiograms

Objective

- To assess the total number of contrast enhanced cine angiographic X-ray runs (angiograms) related to PCI in the Dynamic Coronary Roadmap and control group

Endpoint

- The average total number of contrast enhanced cine angiographic X-ray runs (angiograms) per PCI (from first positioning the interventional guiding catheter in stable coronary position till end of PCI procedure) determined via visual assessment (e.g., on the Philips X-ray system).

Hypothesis

Dynamic Coronary Roadmap reduces the total number of contrast enhanced cine angiographic X-ray runs (angiograms) acquired on average per PCI.

$$H_0: Pop_{Control2} \leq Pop_{DCR2}$$

$$H_a: Pop_{Control2} > Pop_{DCR2} \text{ (Control is shifted to the right of DCR)}$$

Where $Pop_{Control2}$ is the population distribution for the number of contrast enhanced cine angiographic X-ray runs (angiograms) acquired per PCI for the Control group, and Pop_{DCR2} is the population distribution for the number of contrast enhanced cine angiographic X-ray runs (angiograms) acquired per PCI for the DCR group.

IGT Systems	Post-Market Clinical Study Protocol DCR4Contrast Clinical Evidence Study	Doc ID: XCY612-130576 Rev: 02 Page 22 of 33
-------------	-----------------------------------------------------------------------------	---------------------------------------------------

Rationale for choice of hypothesis

Based on pilot study results and the working mechanism of DCR this hypothesis is chosen to measure the effect of DCR on the number of contrast enhanced cine angiographic X-ray runs (angiograms) acquired in PCI.

Analysis

The number of angiographic X-ray runs is discrete and is likely to be not normally distributed, so the objective will be evaluated using a one-sided Wilcoxon-Mann-Whitney test.

All subjects will be included in this analysis.

7.8. Exploratory objectives

7.8.1. Exploratory objective: Contrast Volume per Vessel PCI

Objective

- To assess the iodinated contrast volume used per vessel PCI in the Dynamic Coronary Roadmap and control group

Endpoint

- The average undiluted iodinated contrast volume (in ml) used per vessel PCI (from first positioning the interventional guiding catheter in stable coronary position till end of PCI procedure) measured by an automatic contrast injector. For multi vessel PCI the iodinated contrast volume used per vessel PCI will be determined based on the total PCI contrast volume (from first positioning the interventional guiding catheter in stable coronary position till end of PCI procedure) divided by the number of vessels treated by PCI.

Analysis

The objective will be evaluated using a two-sample equal-variance t-test and cluster analysis.

All subjects will be included in this analysis.

7.8.2. Exploratory objective: Contrast Volume per Stratification Group (1, 2, 3 or more vessel PCI)

Objective

- To assess the total iodinated contrast volume related to PCI per stratification group, i.e., 1 vessel PCI, 2 vessel PCI and 3 or more vessel PCI, in the Dynamic Coronary Roadmap and control group

Endpoint

- The average total undiluted iodinated contrast volume (in ml) used per PCI (from first positioning the interventional guiding catheter in stable coronary position till end of PCI procedure) measured by an automatic contrast injector in each stratification group, i.e., 1 vessel PCI, 2 vessel PCI and 3 or more vessel PCI.

Analysis

The objective will be evaluated using a two-sample equal-variance t-test and cluster analysis.

All subjects will be included in this analysis.

7.8.3. Exploratory objective: Contrast Volume per Simple, Intermediate, Complex PCI subgroup

Objective

- To assess the total iodinated contrast volume related to PCI in subgroups of simple, intermediate and complex PCI (where the SYNTAX score for the vessel(s) treated with PCI will be used as an index for complexity) in the Dynamic Coronary Roadmap and control group

IGT Systems	Post-Market Clinical Study Protocol DCR4Contrast Clinical Evidence Study	Doc ID: XCY612-130576 Rev: 02 Page 23 of 33
-------------	-----------------------------------------------------------------------------	---------------------------------------------------

Endpoint

- The average total undiluted iodinated contrast volume (in ml) used per PCI (from first positioning the interventional guiding catheter in stable coronary position till end of PCI procedure) measured by an automatic injector in subgroups of simple, intermediate and complex PCI. The SYNTAX score for the vessel(s) treated with PCI will be calculated to be used as an index for the anatomical complexity of the PCI [Sianos 2005].

Analysis

The objective will be evaluated using a two-sample equal-variance t-test and cluster analysis.

The iodinated contrast volume usage and related contrast volume usage difference will be binned according to the anatomical complexity of the PCI procedure using the SYNTAX score for the vessel(s) treated with PCI as index for anatomical complexity.

All subjects will be included in this analysis.

7.8.4. Exploratory objective: AKI Incidence

Objective

- To assess the incidence of Acute Kidney Injury (AKI) in the Dynamic Coronary Roadmap and control group (at discharge following standard clinical care)

Endpoint

- The total number and percentage of subjects in which AKI, (defined as an absolute SCr increase >0.3 mg/dl within 48 hours post PCI or a relative SCr increase $>50\%$ within 7 days post PCI, or eGFR decrease $>25\%$ within 48 hours post PCI) is diagnosed after PCI.

Analysis

Multiple AKI definitions exist, which are all based on measuring serum creatinine (SCr, measured via isotope dilution mass spectrometry (IDMS) [Meyers 2006]) or urine output:

- RIFLE (Risk, Injury, Failure, Loss, End stage renal disease) [Bellomo 2004],
- Acute Kidney Injury Network (AKIN) [Mehta 2007], and
- Kidney Disease Improving Global Outcomes (KDIGO) guidelines [KDIGO guidelines AKI 2012].

A recent study [Parsh 2016] showed that the combination of an absolute Serum Creatinine (SCr) increase >0.3 mg/dl within 48 hours post PCI or a relative SCr increase $>50\%$ within 7 days post PCI might be the most optimal definition for AKI.

Using the SCr measurement often the estimated GFR (eGFR) is determined as a measure of kidney function, which can be calculated according to the Modification of Diet in Renal Disease (MDRD) equation or its successor the Chronic Kidney Disease epidemiology (CKD-EPI) equation [Levey 1999, Bellomo 2004, Levey 2006, Levey 2009, Van den Brand 2011, Nyman 2014]. The CKD-EPI equation to estimate the glomerular filtration rate reads [Levey 2009]:

$$\text{eGFR} = 141 \times \min(\text{SCr}/K, 1)^\alpha \times \max(\text{SCr}/K, 1)^{-1.209} \times 0.993^{\text{Age}} \times 1.018[\text{if female}] \times 1.159[\text{if black}],$$

with K=0.7 and $\alpha=-0.329$ if female;
with K=0.9 and $\alpha=-0.411$ if male.

Here min indicates the minimum of SCr/K or 1, and max indicates the maximum of SCr/K or 1.

Based on the eGFR calculation CKD can be classified in 5 stages as indicated in Table 3.

IGT Systems	Post-Market Clinical Study Protocol DCR4Contrast Clinical Evidence Study	Doc ID: XCY612-130576 Rev: 02 Page 24 of 33
-------------	-----------------------------------------------------------------------------	---------------------------------------------------

CKD classification	eGFR (ml/min/1.73m ²)
Stage I (normal renal function)	>60
Stage II (mild – moderate reduction)	45 – 60
Stage III (moderate – severe reduction)	30 – 45
Stage IV (severe reduction)	15 - 30
Stage V (renal failure)	<15

Table 3 CKD classification based on eGFR [Tsai 2014a]

New AKI biomarkers are being investigated such that both renal function and renal damage can be diagnosed early, but even the most promising ones (cystatin C and neutrophil gelatinase-associated lipocalin (NGAL)) are rarely routinely used in the hospital [Ostermann 2016]. Serum creatinine measurement and eGFR calculation are still most commonly used to diagnose AKI, which we will also adopt using the following definition for AKI [Parsh 2016, Bellomo 2004]:

- An absolute Serum Creatinine (SCr) increase >0.3 mg/dl within 48 hours post PCI or a relative SCr increase >50% within 7 days post PCI

OR

- eGFR decrease >25% within 48 hours post PCI

Note that according to [Guideline NVvR 2017] the measurement of SCr/eGFR is valid for:

- Maximally 7 days when the patient has an acute disease or an acute deterioration of a chronic disease;
- Maximally 3 months when the patient has a known chronic disease with stable renal function;
- Approx. 12 months in all other patients

The majority of PCI patients are discharged within 24 hours after the PCI procedure and consequently the SCr measurement is performed within 24 hours post PCI while the SCr levels might still be rising and diagnosis of AKI may be missed as a result.

Furthermore when considering the incidence of AKI in the patient population of this trial (7.1% incidence, but reported from 3% to 19% [Tsai 2014a]) and taking into account the sample size of 394 patients it is not likely this trial will find a significant difference in AKI incidence in the DCR group compared to the control group.

As AKI prevention method adequate pre- and post-hydration with isotonic saline (NaCl 0.9%) should be applied to patients with GFR<60 ml/min/1.73m² as recommended by the ESC/EACTS Guidelines: 1 ml/kg/h 12 h before and continued for 24 h after the procedure (0.5 ml/kg/h if LVEF ≤35% or NYHA >2) [Neumann 2018].

The objective will be evaluated using a two-sample equal-variance t-test.

All subjects will be included in this analysis.

